The study will end at once if severe adverse events associated with CHM occurs or sufficient evidence indicates that adding CHM is not superior to the SMT group. Besides, CHM will discontinue and the final status will be censored in the condition of liver transplantation or the onset of liver cancer. Allocated interventions can be changed upon participant's request. All these changes will be recorded and analyzed based on intention-to-treat (ITT).

Intervention

Standard medical treatment

The SMT include a high-calorie diet; nucleoside analogues for HBV DNA-positive patients; sodium restriction, diuretics and paracentesis combined with albumin infusion for ascites; lactulose and L-ornithine aspartate and lactulose for HE and hyper-ammonia; hemostatic treatment for gastrointestinal hemorrhage; antibiotics for infections and renal replacement for HRS and uremic symptoms. CHM formulas, whatever routes of administration, are prohibited in the SMT group.

Chinese herbal medicine formula

There are two kinds of CHM based on traditional Chinese Medicines (TCM) syndromes. The common components of the two CHM formulas include *Artemisiacapillaris* Thunb (30g), *Salvia miltiorrhiza* Bge (30g), *Rhizoma*

Atractylodis Macrocephalae (30g), Rubia cordifolia L (30g), Sieyesbeckiaorientalis L (30g). Additional four components of Paeoniae Radix Rubra (60g), Gardenia jasminoides Ellis (9g), Hedyotis diffusa Willd (30g), Bletilla striata (15g) are involved for excess syndrome, and five other components of Astragalus membranaceus (30g), Radix Pseudostellariae (15g), Radix Aconiti Lateralis Praeparata (10g), Galli Gigeriae Endothelium Corneum (20g), Polygonum cuspidatum Sieb.et Zucc (15g) are involved for deficiency syndrome. All ingredients are manufactured as a Chinese herbal granule in a specific weight ratio to the raw herb (Beijing Kang Rentang Pharmaceutical Co., Ltd, Beijing, China) in accordance with the quality criteria of Chinese pharmacopoeia in 2015. Patients will take one dosage of CHM granule per day for 8 weeks. For patients who cannot take oral medicine can be switched to colon route by the colonic therapy system (IMS-100A produced by Sunny Medical in Beijing China).

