In addition, patients in the CHM group will also receive daily herbal enema of 100 microliter decoction composed by Radix et Rhizoma Rhei Palmati (Dahuang) 30g and Fructus Mume (Wumei) 30g for 7 days expect the following contraindications: (1) severe hemorrhoid, (2) female patients during menstruation, (3) anal stenosis, (4) artificial anal and (5) cardiac disease.

Outcome measurements

Primary outcome

The primary outcome is transplant-free survival at week 12.

Secondary outcomes

Secondary outcomes include (1) transplant-free survival at week 24, (2) the influence on liver function assessed by MELD score (involving levels of serum bilirubin, creatinine, INR and sodium) at week 12, (3) the influence on liver function assessed by Child-Pugh score (involving the serum bilirubin, coagulation function, albumin and the complication of hepatic encephalopathy and ascites) at week 12. (4) quality of life assessed by WHOQOL-BRIEF at week 12 and (5) the incidence of serious complications (including infections, encephalopathy, HRS, and gastrointestinal bleeding) from week 1 to week 24.

Safety outcomes

Primary vital signs, physical examinations, electrocardiogram and some laboratory tests such as routine blood test, urine test, renal function will be assessed before and after treatment to monitor the safety of this study. Furthermore, adverse events are also recorded in a predesigned case report form (CRF) through the whole study period. An independent safety committee will analyze the incidence and severity of adverse events to identify any unexpected adverse events or mortality in the CHM groups.

Other assessed parameters

Epidemiological characteristics, the details of nucleoside/nucleotide analog therapy, family history of liver disease were collected from patient medical record, the level of HBV DNA, endotoxin, and lymphocyte subsets were tested as well as CLIP-C-ACLF score were computed at week 24 and 48. The plasma level of HBV DNA, endotoxin, and cytokines were tested in ADICO clinical laboratories (Shanghai, China) which is blind to the allocation information. Remnant plasma will be stored at -80°C for ancillary studies. Women of childbearing age will undergo pregnancy test for the eligibility.

Sample size

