The randomized subjects who take at least one dose of CHM or SMT constitute the full analysis set (FAS) and those who complete all the visits constitute the per-protocol set (PPS). An efficacy assessment will be analyzed using FAS and PPS based on the principle of ITT. Subjects who have taken the CHM and been evaluated the safety at least once constitute the safety set (SS), which is used for safety evaluation. The statistical analysis will be performed using SAS 9.0 software (SAS Institute, Cary, NC, USA) by independent data management committee who are blind to the interventions.

Comparison of the two groups is conducted for the continuous variables with *t*-test and the categorical variables or rates with the chi-square test. The Kaplan-Meier overall survival curves will be generated and tested by log-rank. Cox proportional hazards regression model will be adopted to determine the prognostic factors associated with transplant-free survival. Multivariate logistic regression analyses will be adopted to explore factors associated with the incidence of liver-related complications. Subgroup analyses will be done based on the diagnostic criteria of Asian Pacific Association for the Study of the Liver (APASL) and European Association for the Study of the Liver (EASL) guideline.

The last observation carried forward approach was used for missing values. The statistical significance is defined as a two-sided $P < 0.05$.

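### No rule says which MELD and Child-Pugh values count after a transplant or death before week 12, so the literal analysis lets a graft score pass as improved liver function

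*Combined protocol and SAP*

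**What the plan says.** Under Secondary outcomes, the combined protocol and SAP lists "the influence on liver function assessed by MELD score" and, as the next item, "the influence on liver function assessed by Child-Pugh score", both at week 12. The primary outcome is transplant-free survival at the same week.

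Under Criteria for discontinuing or modifying allocated interventions, it says "CHM will discontinue and the final status will be censored in the condition of liver transplantation or the onset of liver cancer". After allowing a participant to ask for a change of intervention, the same paragraph ends: "All these changes will be recorded and analyzed based on intention-to-treat (ITT".

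Data management and Statistical methods defines the main analysis population this way: "The randomized subjects who take at least one dose of CHM or SMT constitute the full analysis set (FAS". The per-protocol population is narrower and depends only on attendance: "those who complete all the visits constitute the per-protocol set (PPS". Efficacy is analysed in both sets on the ITT principle, with a t-test for continuous variables and LOCF for missing values. Neither set excludes transplanted patients, and no section says whether a score taken after transplantation is used, replaced or left out.

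**The concern.** A patient transplanted in, say, week 4 and alive at week 12 has a measurable bilirubin, INR, creatinine, sodium and albumin. Those values describe the donor liver. Averaged into the allocated arm, a good graft score reads as a good effect of treatment on liver function. By the primary endpoint's name, the same event is a failure there.

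If the herbal treatment avoided transplants, the control arm would collect more graft scores and the comparison would be tilted against the treatment. If it led to more transplants, the tilt would favour it. Death raises the same question. A patient who dies before week 12 has no score, and the only rule that reaches this case is LOCF, which would enter a score from before death as a week-12 result. The Sample size section cites 30.87% mortality at 8 weeks under standard treatment, so these cases would not be rare.

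**Working it through.** The plan gives no figure on this point to reproduce. The check is a reading of the rules, followed by an illustration of size.

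**1. What enters for a patient transplanted before week 12 and alive at week 12**

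| Reading | Value used | Effect on the arm with more transplants |
|---|---|---|
| Literal: the score is observed, so LOCF is not triggered; censoring concerns survival status | Graft score | Looks better |
| Censoring of final status is extended to the scores, and LOCF fills the gap | Last pre-transplant score | Looks worse, if those scores are worse than the rest |

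The first is the more natural reading. Censoring is a time-to-event operation, and a t-test on a week-12 score has no censoring step. The second is not excluded. The per-protocol set does not settle the matter, because a transplanted patient who completes all visits stays in it.

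**2. Size under the literal reading**

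Assumed, not from the documents: native-liver MELD mean 18, SD 8; graft mean 9, SD 3; 170 evaluable per arm; no treatment effect on native-liver score. For orientation on the 170: 255 × 0.9 = 229.5 after the plan's attrition, and 229.5 × (1 − 0.3087) = 158.7 if the cited control mortality applied.

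- Shift = (difference in transplant shares) × (18 − 9).
- Variance in an arm with share p: V(p) = (1 − p) × 64 + p × 9 + p(1 − p) × 81. This gives V(0.05) = 65.1, V(0.10) = 65.8 and V(0.15) = 66.1.
- SE = √[(V₁ + V₂)/170], about 0.88 in both unequal cases.
- Rejection probability ≈ Φ(shift/SE − 1.96) + Φ(−shift/SE − 1.96).

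| Shares | Shift | Shift/SE | Rejection (formula) | Simulation, 5,000 replicates |
|---|---|---|---|---|
| 5% v 5% | 0 | 0 | 5% | 5.7% |
| 10% v 5% | 0.05 × 9 = 0.45 | 0.51 | 8% | 8.0% |
| 15% v 5% | 0.10 × 9 = 0.90 | 1.02 | 18% | 17.7% |

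**3. Sensitivity to the assumptions**

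Take 229 per arm, a common SD of 8 to 10 and a native-minus-graft gap of 8 to 16 points. The SE is SD × √(2/229), that is 0.75 to 0.93.

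- 10% v 5%: shift 0.4 to 0.8 points, rejection 7% to 19%.
- 15% v 5%: shift 0.8 to 1.6 points, rejection 14% to 57%.

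**4. Size under the LOCF reading**

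Assume carried-forward scores with mean 28 and SD 6, and otherwise the inputs of step 2. Shares of 15% v 5% give 0.10 × (28 − 18) = 1.0 point in the opposite direction, with rejection 19.7% by simulation.

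No size was computed for Child-Pugh. The mechanism is the same.

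**The case against.** A reader might infer that the plan does score the graft, and that the arm with more transplants will therefore look better. The documents do not establish this. ITT and the full analysis set fix who is analysed and in which arm, not which measurement is used after an event. The ITT sentence also directly follows one about changes at the participant's request. Censoring plus LOCF can be read as substituting a pre-transplant score, which can turn the direction round. This objection stands: the direction is unsettled. It does not clear the plan, because two tenable readings give opposite biases.

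The size can also be challenged. Every transplant rate, mean and SD is assumed. The larger figures need a two- or three-fold difference in transplant share, which would itself reflect a treatment effect or a difference in management, and nothing in the documents indicates one. Even then the shift is below one point against an assumed SD of 8. This stands too. However, a trial that aims to change transplant-free survival cannot assume equal transplant shares.

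Finally, the plan says status is censored at transplantation, so even the treatment of transplant as a primary-outcome failure rests on the endpoint's name. That conflict needs resolving in its own right. It does not supply the missing rule for the scores.

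**Conclusion.** The gap is real. For MELD and Child-Pugh at week 12, the plan states no handling of transplantation, and none of death beyond the general LOCF rule. Followed literally, it allows graft scores to count as improved liver function. That the bias will occur, or in a particular direction, does not follow from the text: it depends on the reading chosen and on unequal transplant shares. On the assumptions in step 2, the literal reading shifts mean MELD by about 0.45 points at 10% v 5% (false-positive rate about 8%) and about 0.9 points at 15% v 5% (about 18%). Equal shares give no bias from graft scores. False-positive here means rejection with no effect on native-liver scores. The point concerns secondary outcomes only, but it should be settled before the data are seen.

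**What to change.** Add to the statistical methods:

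- MELD and Child-Pugh values measured after transplantation are not used for secondary outcomes (2) and (3).
- LOCF is not used to fill in scores after transplantation or death.
- Arms are compared by a rank test on a composite. Death before week 12 ranks worst, transplant before week 12 ranks next (or ties with death), and patients alive with their native liver are ranked by week-12 score.
- Mean scores in patients alive with their native liver are reported as description only.

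The place of death must be written down. If only transplant were ranked worst, transplanted survivors could fall below patients who died.

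The cost is a few sentences and a small programming rule, with no new data. There is a small downside: the main result becomes a rank comparison, not a mean difference in points, and it partly reflects the primary events. The descriptive means in native-liver survivors keep the scores interpretable, but they compare groups selected after randomisation and should not carry the inference.

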Study Protocol

Official Title of the study: Effectiveness and safety of Chinese herbal medicine for hepatitis B virus-related acute-on-chronic liver failure: A multi-center, randomized and controlled trial

NCT number: not yet assigned

Date of the document: June 21, 2018

This prospective, multi-center, parallel, centrally randomized controlled trial was designed in accordance with the Consolidated Standards of Reporting Trials (CONSORT) and Standard Protocol Items: Recommendations for Interventional Trials (SPIRIT) guideline, which is led by the principal investigator from 302 military hospital in Beijing, will be carried out from September 2018 and December 2020 among 16 tertiary academic hospitals in China. Patients with hepatitis B virus (HBV) related Acute-on-chronic liver failure (ACLF) will be randomly allocated to the Chinese herbal medicine (CHM) group or the standard medical treatment (SMT) group in a 1:1 ratio. The last patient will be enrolled before August 2019 to make sure the availability of 48 week's survival status by the end of this study. We will decide whether to expand additional institutions to guarantee adequate enrolments after interim assessment of effective participant numbers around December 2018. Patients in the SMT group will receive the standard medical treatment, and patients in the CHM group will receive rhubarb decoction enema for 1 week and CHM for 8 weeks additionally. All patients will be followed at pre-designed time points after 8 weeks' observational period until August 30, 2020 for the primary outcome and secondary outcomes.

The study is consistent with Good Clinical Practice(GCP) guidelines and has been approved by 302 military hospital ethics review committee (2018007D). Written informed consent is requisite to be signed by the patients or the authorized person under the willingness. The privacy and data of all participants will be protected carefully before, during and after the trial.

Patients will be consented and enrolled by co-principal investigators at each institution and managed by care providers including residents, attending physicians and nurses according to the protocol. Most of the patients will be treated in hospital for 8 weeks so clinicians can supervise the administration of CHM, in addition, the policy of reimbursement filed by the lab results at determined time points will boost the regular follow-up of this study.

Diagnostic criteria

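### The plan states only a week-12 quality-of-life assessment and no baseline, so the comparison is unadjusted and the carry-forward rule has no stated earlier score to use

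*Combined protocol and SAP*

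**What the plan says.** WHOQOL-BRIEF appears once in the combined protocol and SAP, in the Secondary outcomes section: "quality of life assessed by WHOQOL-BRIEF at week 12". No section names an entry assessment, a change score or a baseline covariate for it. The Safety outcomes section does provide for pre-treatment measurement, but of vital signs, examinations, electrocardiogram and laboratory tests, which "will be assessed before and after treatment to monitor the safety of this study". Quality of life is not in that list.

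The Data management and Statistical methods section supplies the analysis: "Comparison of the two groups is conducted for the continuous variables with *t*-test". The only missing-data rule is general: "The last observation carried forward approach was used for missing values". On analysis populations it says: "An efficacy assessment will be analyzed using FAS and PPS based on the principle of ITT". The full analysis set is the randomised patients who received any study treatment.

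The documents contain no table of visits and assessments. The opening description refers to one without listing it: "All patients will be followed at pre-designed time points after 8 weeks' observational period until August 30, 2020".

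**The concern.** A questionnaire score exists only if someone administers the questionnaire. Bilirubin and coagulation are known at entry because the Diagnostic criteria require them. Nothing comparable guarantees an entry WHOQOL-BRIEF score, and a site working from this text has no instruction to collect one. Three things follow if none is collected:

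- Week-12 scores are compared without the covariate likely to explain most of their variation, so the estimate is less precise than it need be.
- Imbalance in starting quality of life can be neither examined nor adjusted for, and patients who lack a week-12 score cannot be described by where they started.
- The missing-data rule, combined with an analysis of all treated randomised patients, calls for a value that is not there.

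A score from before allocation cannot be recovered later, so the matter has to be settled before enrolment.

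**Working it through.** The plan gives no standard deviation, effect size or power for quality of life, so it has no figure of its own to reproduce. The check has four parts.

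**1. The carry-forward rule against the stated times.** The rule needs an observation before week 12, and none is stated for WHOQOL-BRIEF.
- If none is taken, a patient who misses week 12 has nothing to carry and the rule cannot be applied.
- If a baseline is taken, the rule can be applied, but it assigns a score from the acute illness to week 12, including for patients who died.

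**2. Precision lost without baseline adjustment.** With correlation r between baseline and week-12 scores, analysis of covariance multiplies residual variance by 1 − r² and interval width by √(1 − r²). The documents give no r, so a range is assumed:
- r = 0.3: variance 0.91, width 0.954 (about 5% narrower)
- r = 0.5: variance 0.75, width 0.866 (about 13% narrower)
- r = 0.6: variance 0.64, width 0.80 (20% narrower)

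**3. Deaths before week 12.** Inputs from the Sample size section: 255 per group and 30.87% 8-week mortality on standard medical treatment (SMT). For the Chinese herbal medicine (CHM) arm, assume the −12% is the expected absolute difference: 30.87% − 12% = 18.87%.
- SMT: 255 × 0.3087 = 78.7
- CHM: 255 × 0.1887 = 48.1
- Total: 126.8 of 510 = 24.9%

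If CHM mortality equalled the control rate, the total would be 2 × 78.7 = 157.4, or 30.9%. Both counts stop at week 8, because the documents give no rate for weeks 8 to 12.

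The 18.87% is an assumption because the sample size does not confirm it. Comparing 30.87% with 18.87% at two-sided 0.05 and 80% power needs 203 per arm, or 203/0.90 = 226 after attrition. With a continuity correction this is 219, or 219/0.90 = 244. Neither is 255. Setting 30.87% in both arms with a 12-point margin (no true difference, one-sided 0.025) gives 233, then 233 × 1.10 = 257 or 233/0.90 = 259, which is closer.

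**4. Detectable difference.** Apply the planned 10% attrition to the week-8 survivors, using the assumed CHM rate:
- SMT: 255 × 0.90 × 0.6913 = 158.7
- CHM: 255 × 0.90 × 0.8113 = 186.2
- Unadjusted, 80% power: (1.960 + 0.842) × √(1/158.7 + 1/186.2) = 0.303 SD
- Adjusted: 0.303 × 0.954 = 0.289 SD at r = 0.3; 0.303 × 0.866 = 0.262 SD at r = 0.5; 0.303 × 0.80 = 0.242 SD at r = 0.6

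**The case against.** The strongest objection is that an outcome time point is not a schedule. The Secondary outcomes section treats other measures in the same way: it lists "the influence on liver function assessed by MELD score (involving levels of serum bilirubin, creatinine, INR and sodium) at week 12" and words Child-Pugh similarly, yet much of what those scores need is measured at entry. HBV DNA appears with weeks 24 and 48 under Other assessed parameters, although the standard treatment depends on knowing HBV DNA status earlier. The document plainly leaves out baseline measurements that must take place. A reader might infer that quality of life will be measured at week 12 and never before, and so that carry-forward must fail. The documents do not support that: they leave other times unspecified, and the failure depends on no earlier score being taken. This part of the objection stands.

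A reader might also infer that the comparison is invalid because chance imbalance could pass for a treatment effect. That does not follow. Under 1:1 randomisation the standard error of the unadjusted difference already allows for chance imbalance. This also stands.

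Third, a baseline does not cause or cure the missing scores of patients who die, and adding one while keeping carry-forward would turn a rule that may not be executable into one that misleads. This stands and shapes the fix.

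It can also be said that this is one of five secondary outcomes, and that at r = 0.3 the gain is only about 5% of interval width. Both are true. They limit the importance of the point but do not remove it, given how little the change costs.

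**Conclusion.** The point holds as a gap in specification with a measurable cost. The plan states no WHOQOL-BRIEF score before week 12, compares arms without adjustment, and has a missing-data rule with no stated score to work on. The cost is the 5% to 20% of interval width shown above, which rests entirely on the assumed correlations, together with the lack of any stated score to describe patients without a week-12 value.

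The proportion dying before week 12, about a quarter, rests on the stated control rate and on reading −12% as the expected absolute difference. It shows how much weight the missing-data rule must bear for this outcome; it does not measure harm done by lacking a baseline. Comparing scores only among survivors carries its own selection problem if survival differs by arm, with or without a baseline.

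The documents describe no placebo, so patients probably know their arm, but that is an inference. A baseline would not remove any resulting bias in self-report. The primary outcome is unaffected. The change is worth making before enrolment.

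**What to change.** - **Schedule.** Administer WHOQOL-BRIEF in both arms after consent and before the allocation envelope is opened, or say so if this is already intended. Record the reason whenever it cannot be completed.
- **Analysis.** Replace the t-test for this outcome with analysis of covariance of the week-12 score on arm and baseline score. Use a missing-indicator for absent baselines; because the baseline precedes allocation, its absence cannot depend on arm.
- **Missing scores and deaths.** Do not apply last observation carried forward to this outcome. Report it in patients alive at week 12, show deaths and missing scores by arm, and add a sensitivity analysis that ranks death as the worst outcome.

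The cost is one short questionnaire per patient and a few lines in the plan. Some patients with encephalopathy will be unable to complete it at entry. Because consent may come from an authorised person, there may be others, and the documents do not allow their number to be estimated.

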The proposed -12% superiority margin of 8-week mortality rate was chosen based on our previous results of 30.87% in the SMT group. Considering a power of 0.80 and 10% of attrition rate, 255 subjects are needed for each group to achieve the significance level of 0.05 in assessing the difference between the two groups.

Randomization

The eligible patients will be randomly allocated to the SMT group and CHM group in a 1:1 ratio. The sealed numbers are generated by a computerized random number generator with statistical analysis system (SAS) software by an independent statistician from the center of clinical evaluation in China Academy of Chinese medical sciences (Beijing, China) and are concealed using opaque envelopes.

Trial monitoring

Trial monitoring is assumed by an independent Contract Research Organization so as to verify that: (1) The rights and well-being of human subjects are protected. (2) The reported trial data are accurate, complete, and verifiable from source documents. (3) The conduct of the trial is in compliance with the currently approved protocol/amendment(s), with GCP, and with the applicable regulatory requirement(s). Monitors should be appropriately trained and have the scientific and/or clinical knowledge needed to monitor the trial adequately. A risk-based monitoring strategy is developed in this trial, which includes on-site and centralized monitoring, which is more likely than routine visits to all clinical sites and 100% data verification to ensure subject protection and overall study quality. On-site monitoring is an in-person evaluation carried out by the monitor at the sites at which the clinical investigation is being conducted. Centralized monitoring is a remote evaluation carried out at a location other than the sites at which the clinical investigation is being conducted. Key monitoring processes include subject inclusion process; implementation of the inclusion criteria; source data verification; data integrity, etc.

Data management and Statistical methods

Data entry will be conducted by two independent administrators using online electronic CRF for accuracy and consistency. At the end of the study, the database will be locked and analyzed under the agreement of principal investigator and statistician, who are privileged to access the final trial dataset.

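### Laboratory, ECG and vital-sign safety has no dated after-treatment assessment and no rule for early death or stopping, so with LOCF about a quarter of patients may be dropped or counted as unchanged

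*Combined protocol and SAP*

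**What the plan says.** The Safety outcomes section covers "Primary vital signs, physical examinations, electrocardiogram and some laboratory tests such as" the items that follow: "routine blood test, urine test, renal function will be assessed before and after treatment to monitor the safety of this study". Treatment in the CHM arm is long relative to that two-point scheme: "Patients will take one dosage of CHM granule per day for 8 weeks", with a daily enema for the first 7 days. No section gives an on-treatment time for these measurements, a date for the second one, or a rule for patients who die or stop early.

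The same section also provides that "adverse events are also recorded in a predesigned case report form (CRF) through the whole study period", and that "An independent safety committee will analyze the incidence and severity of adverse events to identify any unexpected adverse events or mortality in the CHM groups". The fifth secondary outcome is "the incidence of serious complications (including infections, encephalopathy, HRS, and gastrointestinal bleeding) from week 1 to week 24".

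Three provisions elsewhere bear on the point. The Sample size section sets its margin for 8-week mortality "based on our previous results of 30.87% in the SMT group". Data management and Statistical methods applies LOCF to missing values, with no exception for safety data or for death. It also limits the safety set to patients who took CHM and had at least one safety evaluation.

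**The concern.** In a disease where the plan expects nearly a third of control patients to die within the treatment period, a two-point assessment needs a rule for those who never reach the second point. Without one, the analyst has two options, and both mislead. Dropping these patients leaves a before/after comparison in survivors. Carrying their baseline forward records a patient who deteriorated and died as having no laboratory change. Either way the result tends to look reassuring, because the patients most likely to have had a renal or cardiac abnormality contribute nothing to it.

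A comparison between arms has a second difficulty. If CHM alters mortality, as the trial hopes, the share of patients without a second value differs by arm, and the patients left for comparison are no longer alike. As the safety set is written, there is no SMT group to compare with at all.

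**Working it through.** The plan states no figure for completeness of safety data, so there is none to reproduce. The check sizes the group that may lack a second value.

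**Inputs**
- Patients per arm: 255, 1:1 allocation (Sample size; Randomization). I take 255 as given. The percentages below do not depend on it.
- SMT 8-week mortality: 30.87% (Sample size).
- CHM 8-week mortality: not stated. Reading the 12% margin as an absolute reduction gives 30.87% − 12% = 18.87%.
- Assumptions not in the documents: the second assessment is at week 8, and none is made at early stopping.

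**Expected number without a second value** = patients × 8-week mortality
- SMT: 255 × 0.3087 = 78.7, about 79. Survivors: 255 − 78.7 = 176.3.
- CHM: 255 × 0.1887 = 48.1, about 48. Survivors: 255 − 48.1 = 206.9.
- Both arms: (78.7 + 48.1) / 510 = 24.9%.

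**Sensitivity to CHM mortality** (SMT held at 30.87%)

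| CHM mortality | CHM deaths | Both arms, share of 510 |
|---|---|---|
| 10% (assumed) | 25.5 | (25.5 + 78.7) / 510 = 20.4% |
| 18.87% (12% absolute) | 48.1 | 24.9% |
| 25% (assumed) | 63.8 | (63.8 + 78.7) / 510 = 27.9% |
| 30.87% (no effect) | 78.7 | 30.9% |

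If the 12% were relative, CHM mortality would be 0.3087 × 0.88 = 27.2%, which lies inside this range.

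**Effect of LOCF from baseline.** A patient with only a baseline value contributes a change of zero. If the mean change among survivors is *d*, the mean over all CHM patients becomes (1 − 0.1887) × *d* = 0.81*d*, and over all SMT patients (1 − 0.3087) × *d* = 0.69*d*. The same change in survivors is therefore shrunk in both arms, and by different amounts, through mortality alone.

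**What the other provisions would catch.** Adverse-event recording catches a laboratory or ECG change if someone reports it as an event; no section says when such a change becomes one. The safety committee analyses adverse events and mortality, so it depends on the same reporting. The complications outcome names infection, encephalopathy, HRS and gastrointestinal bleeding from week 1. It does not name ECG findings, blood-count changes or creatinine rises short of HRS.

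**The case against.** The strongest reply is that the protocol does monitor safety during treatment. Adverse events are recorded throughout, an independent committee reviews them and mortality, HRS and bleeding are counted from week 1, and the trial is to end if severe adverse events associated with CHM occur. Most patients are in hospital for the 8 weeks. The second assessment is undated, so it may well be made when a patient stops.

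Much of this stands. A reader might infer that objective safety is measured only in 8-week survivors and that toxicity during treatment, or in patients who die, is missed. The documents do not support that: an assessment at early stopping is not excluded, and clinically evident harm has several routes into the record. LOCF, read literally, also means that early deaths are not necessarily dropped.

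Nor can one assume that suitable tests are already scheduled. The protocol's opening section says that "the policy of reimbursement filed by the lab results at determined time points will boost the regular follow-up of this study", but it lists neither the weeks nor the tests and ties them to follow-up. Nothing shows that a test is done at the end of the enema course.

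The reply does not close the gap. Each safeguard depends on an abnormality being noticed and reported, and no placebo or sham enema is described, so reporting is presumably done with knowledge of the allocation. LOCF alters the form of the problem without solving it.

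**Conclusion.** The point holds as one of under-specified timing combined with an unsuitable missing-data rule, and it should be corrected. Followed literally, the plan can give a falsely reassuring laboratory and ECG result. The 25% figure is conditional on all three assumptions: a second assessment at week 8, none at early stopping, and the absolute reading of the 12%. In the safety set as written, which is CHM only, the affected group is about 48 of 255, or about 26 to 79 over the same assumed mortality range.

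What could be lost is limited to laboratory or ECG changes not reported as adverse events, and renal deterioration short of HRS, mainly in the sickest patients. It does not follow that CHM toxicity would go undetected.

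**What to change.** 1. Define the after-treatment value as the week 8 assessment or, for patients who die or stop earlier, the last assessment before that.
2. Exempt safety data from carrying baseline forward. Report patients with no post-baseline value as such, by arm.
3. Enter in the CRF the on-treatment laboratory, ECG and vital-sign results already obtained during the hospital stay, and list the time points and tests that the opening section leaves unnamed.
4. Report in both arms, over weeks 0 to 8, the worst post-baseline value and the proportion with a shift on a named grading scale.
5. Include SMT patients in the safety set; without this, item 4 cannot be done.

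The cost is CRF fields, more data entry and revised safety-table wording. New tests are not required.

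There is a statistical downside. A worst value depends on how often and how long a patient is tested, so an arm that survives longer or is tested more has more chances of an extreme result, and values near death partly reflect the disease. The main comparison should therefore use common nominal time windows in both arms, with number of tests and time at risk reported by arm.
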